### **5.3 Tolerability Variables**

Tolerability assessments by each subject will include the following:

- Study drug sensation assessment at Visit 5 (Postoperative Day 8)
- Ocular symptoms
  - Photophobia, itching, tearing, and discharge

See [Appendix B](#) for details on the tolerability assessment procedures and grading scales.

### **5.4 Appropriateness of Variables**

In this study, all assessments and evaluations to assess the efficacy and safety of LE gel 0.38% are considered standard practice in the field of ophthalmology for diagnosis and management of postoperative inflammation and pain following routine cataract surgery.

### **5.5 Risk Assessment**

The subjects will be informed of any risks in the ICF. If additional risks are identified, the Sponsor will notify the Investigators.

## **6.0 STUDY METHODS**

The following assessments must be performed by an ophthalmologist as required at a given study visit:

- Elicitation and recording of AEs (ophthalmologist or qualified designee (eg, sub-investigator)
- Slit-lamp examination (biomicroscopy)
- Dilated ophthalmoscopy

- IOP assessments

## 6.1 Study Visits

Refer to [Appendix A](#) for a schedule of visits and parameters and [Appendix B](#) for methods of clinical evaluation.

Following identification of a potential subject, the Investigator or designee will explain the purpose of the study, procedures, risks/benefits, and subject responsibilities to the potential subject. The subject's willingness and ability to meet the follow-up requirements of the study will be determined. If the subject chooses to participate in the investigation, written informed consent will be obtained. The subject and the person obtaining written consent will sign and date the IRB-approved ICF. At the point of signing the ICF, the subject is considered part of the study population. The original signed document(s) will be retained in the subject records, and a copy will be provided to the subject. In addition, HIPAA authorization must be obtained from each subject.

### 6.1.1 Visit 1: Screening Assessment

***NOTE: Visit 1 shall occur no earlier than 14 days prior to surgery. The Visit 1 date will be the date on which the first screening assessment is performed. The informed consent date may be the same as or prior to visit 1 (screening assessment date).***

- Obtain written informed consent and HIPAA authorization
- Determine if the subject meets preliminary eligibility criteria
  - Collect demographic information
  - Collect current and relevant medical and ophthalmic history
  - Identify concomitant medications used
  - Perform a urine pregnancy test, as applicable
- If the subject meets the preliminary eligibility criteria, the following assessments will be performed:
  - Perform a clinical assessment of ocular symptoms
  - Perform assessment of pin-holed Snellen VA
  - Perform biomicroscopy assessments
  - Perform IOP measurement (measurement of IOP must occur after the assessment of ocular symptoms and biomicroscopy)
  - Perform dilated fundus examination
- Collect and record AEs

***NOTE: Surgery will be scheduled to occur ≤ 14 days of the first Screening Assessment Visit. Screening and surgery cannot take place on the same day.***

6.1.2 Visit 2: Surgery ( $\leq$  14 days of Visit 1/first Screening Assessment performed)

The following must be performed prior to the surgery:

- Collect and record AEs and changes in concomitant medications.

**NOTE:** *Following surgery, subjects may only receive antibiotics and will be scheduled to return in 18 to 34 hours to determine if they have sufficient ocular inflammation to be included in the study (see Inclusion Criterion #12). Subjects who do not receive a posterior chamber IOL or who, in the Investigator's opinion, have complications such that it is not in the subject's best interests to continue in the study are to be considered screen failures.*

**NOTE:** *If during the surgery it is determined that additional manipulations, such as pupil stretching or the use of iris hooks or peripheral relaxing corneal incisions are required, the subject is not eligible to participate in the trial.*

6.1.3 Visit 3: Postoperative Day 1 (Randomization [18 to 34 hours post-surgery])

**NOTE:** *Post-surgery visits should be scheduled so that IOP can be assessed within  $\pm$  2 hours of the time of IOP assessment on Visit 1.*

- Perform a urine pregnancy test, as applicable
- Perform a clinical assessment of ocular symptoms
- Perform assessment of pin-holed Snellen VA
- Perform biomicroscopy assessments
  - Assess AC cells (refer to [Appendix B](#))
    - If the AC cell grade is  $\geq$  2, then the subject is eligible and will be randomized.
    - If the AC cell grade is  $<$  2, then the subject is not eligible and will be a screen failure.
- Perform IOP measurement
  - IOP should be assessed within  $\pm$  2 hours of the time IOP was assessed at Visit 1 (Screening). Measurement of IOP must occur after the assessment of ocular symptoms and biomicroscopy.
  - If a one-time intervention is necessary to reduce IOP prior to randomization (eg, 'burping' the paracentesis, Diamox, or topical hypotensive agent) and the pressure returns to normal, the subject can be randomized into the study. The AE and intervention should be recorded on the appropriate logs (eg, Adverse Event, Concomitant Medication, and Ocular Surgical Intervention) and the final IOP measured prior to randomization should be recorded in the eCRF.
- Randomize eligible subjects by assigning the next applicable subject kit number
- Dispense study drug kit to the subject

- Instruct the subject to instill 1 drop of study drug into the study eye according to the instructions provided with the kit.
  - Subjects should instill their initial dose while in the clinic to ensure that they understand and are able to follow instructions for instillation.
  - The Investigator and study staff involved in assessments of safety and efficacy must not be present during the in-office study drug instillation.
  - Remind subjects to instill all doses on Day 1 even if the interval between doses is shorter than described in the kit instructions.
  - For those subjects receiving a topical antibiotic, remind the subject that the topical antibiotic drops must be instilled a minimum of 15 minutes BEFORE study drug application.
- Collect and record AEs and changes in concomitant medications
- Provide a Study Drug Administration Diary to the subject. Instruct the subject to record each instillation in the diary and to bring the diary and study drug (all bottles) to the next visit. Remind the subject that no other information should be recorded in the diary.

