
Change from baseline (Visit 3) in AC cells and flare composite score (Anterior Chamber Reaction), as well as individual cells and flare scores, will be analyzed using both continuous and discrete statistical methods by treatment and visit, with missing data imputed by LOCF.
 
Analysis of complete resolution of AC cells, and Grade 0 pain at each visit will be conducted using a Pearson Chi-squared test, with missing data imputed as failures, and also with missing data imputed by LOCF. Similar analyses will be performed for complete resolution of AC cells and flare combined and for flare separately.
 
Other secondary or exploratory efficacy analyses may also be carried out as described in the study Statistical Analysis Plan.
 
Safety Endpoints
 
Tolerability endpoints will be summarized using discrete summary statistics by visit and treatment group.
 
Treatment-emergent AEs (TEAEs), defined as AEs that occur after the first dose of study medication, will be summarized prior to and after rescue medication and as ocular and non-ocular events separately. Ocular events will be summarized for treated eyes and fellow eyes separately. Non-treatment-emergent events will be presented only in the listings, with ocular and non-ocular events displayed separately.
 
A 95% confidence interval around the difference between treatment groups in the incidence of treatment-emergent AEs >1% will be constructed using asymptotic normal approximations.
 
Biomicroscopy and Fundoscopy
 
Biomicroscopy findings will be summarized at each visit and at the worst case on treatment by subject and parameter, both prior to and after rescue medication use. Incidence of treatment-emergent events will be tested using both a Pearson Chi-squared test and a Cochran Mantel-Haenszel test
 
Fundoscopy measures will be summarized for screening and at Visit 6 (Postoperative Day 15) or upon study exit for early termination, for all subjects and subjects that had no rescue medication use. Incidence of treatment-emergent events will be tested using a Pearson Chi-squared test and a Cochran Mantel-Haenszel test adjusted for study sites.
 
Visual Acuity
 
Pinhole Snellen VA will be summarized at each visit as a categorical variable (20/20, 20/40, etc) and as a line change from baseline (Visit 3). Worst line change from baseline will also be presented. Visual acuity will be presented prior to and after rescue medication use. Subjects presenting a line change of >2 lines will be tested using a Pearson Chi-squared test and a Cochran Mantel-Haenszel test adjusted for study sites.
 
IOP
 
Intraocular pressure will be summarized at each visit and worst case on treatment for each subject using both continuous summaries (including change from baseline [Visit 3]) and discrete summaries. Results prior to and after rescue medication use will be presented separately. Discrete summaries will include:
 
 
• The proportion of subjects with change in IOP from screening at any visit <math>\geq 5</math> and <math>\geq 10</math> mm Hg
 
• The proportion of subjects with change in IOP from baseline at any visit
 
	

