### **7.0 ADVERSE EVENTS**

#### **7.1 Definition of Adverse Events**

- Any untoward medical occurrence (including an abnormal laboratory finding) in a subject participating in a clinical study that does not necessarily have a causal relationship with the study protocol and/or procedure or with the study treatment.
- Any unfavorable and unintended sign (including an abnormal laboratory finding), symptom, or disease with onset following the signing of informed consent through study exit, whether or not considered related to the study. An AE can also include a progression/worsening of underlying disease, hypersensitivity, and extravasation.
- Events occurring from drug overdose, whether accidental or intentional, events occurring from drug abuse, drug misuse, drug interactions, drug dependency, events occurring from drug withdrawal, and medication errors.

- A treatment-emergent AE (TEAE) is defined as an AE with a start date on or after the first dose of study drug, or that worsened following first administration of study drug.

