### 7.3 Reporting Adverse Events and Follow-up

Throughout the course of the study, efforts will be made by the Investigator to remain alert to possible AEs that are either systemic or ocular in nature. The period of observation for collection of AEs extends from the time the subject gives informed consent until the last study visit or discontinuation from the study. The first concern will be the safety of the subject, and appropriate medical intervention will be made.

The Investigator or designee will elicit reports (ie, via direct questioning, observation, clinical evaluation) of AEs from the subject at each study visit and record all AEs. The Investigator will document the dates of onset, progress, outcome, and resolution of such AEs. The Investigator will also provide an assessment of all AEs as to the severity, causal relationship to study drug, and causal relationship to study protocol.

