### 8.5.1.2 Safety Endpoint Analyses

Safety endpoints will be summarized using discrete summary statistics by visit and treatment group.

Treatment-emergent AEs (TEAEs), defined as AEs that occur after the first dose of study medication, will be summarized prior to and after rescue medication and as ocular and non-ocular events separately. Ocular events will be summarized for treated eyes and fellow eyes separately. Non-treatment-emergent events will be presented only in the listings, with ocular and non-ocular events displayed separately.

A 95% confidence interval around the difference between treatment groups in the incidence of treatment-emergent AEs  $> 1\%$  will be constructed using asymptotic normal approximations.

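### Sections 7.1 and 8.5.1.2 define treatment-emergent AEs differently, so an IOP rise treated before randomization at Visit 3, or an ongoing AE that worsens on drug, is counted under one rule and not the other

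*Combined protocol and SAP*

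**What the plan says.** Visit 3 (Section 6.1.3, repeated in the synopsis) provides for a pressure spike: "If a one-time intervention is necessary to reduce IOP prior to randomization", the subject may still be randomized once the pressure is normal again. The paperwork is specified: "The AE and intervention should be recorded on the appropriate logs (eg, Adverse Event, Concomitant Medication, and Ocular Surgical Intervention"). Later in the same visit comes the first dose: "Subjects should instill their initial dose while in the clinic".

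On AE recording, Section 7.3 says: "The Investigator will document the dates of onset, progress, outcome, and resolution of such AEs". It names dates and does not mention times.

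Treatment-emergent is then defined twice:

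- Section 7.1: "A treatment-emergent AE (TEAE) is defined as an AE with a start date on or after the first dose of study drug". The sentence goes on to include AEs that worsen after the first administration.
- Section 8.5.1.2, with the same wording in the synopsis: "Treatment-emergent AEs (TEAEs), defined as AEs that occur after the first dose of study medication". There is no worsening clause.

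The classification decides where an event is reported. Section 8.5.1.2 plans, for TEAEs above 1%, "A 95% confidence interval around the difference between treatment groups in the incidence of treatment-emergent AEs", based on a normal approximation. For everything else, the synopsis and 8.5.1.2 both state: "Non-treatment-emergent events will be presented only in the listings".

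**The concern.** The protocol itself produces AEs on the boundary between the two definitions. A spike found and treated at Visit 3 is a logged AE that can carry the same calendar date as the first dose, and Visit 3 is the first scheduled IOP reading after surgery (Appendix A). One definition works by start date, the other by order in time. Only one of them covers worsening. A programmer following 7.1 and a programmer following 8.5.1.2 would produce different ocular TEAE tables from the same data, and both could point to current protocol text.

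At stake are the reported ocular TEAE rates and the intervals around their differences. This matters somewhat more than usual because the Introduction names IOP elevation as a common corticosteroid risk and Section 7.3.3 treats IOP increase as an AE of special interest.

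**Working it through.** **Step 1. Apply both definitions to the possible events.**

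| Event | Section 7.1 | Section 8.5.1.2 and synopsis |
|---|---|---|
| IOP rise treated and resolved before randomization, onset dated to Visit 3 | TEAE (start date equals first-dose date) | Not a TEAE (occurred before the dose) |
| Same event, onset dated to the day of surgery | Not a TEAE | Not a TEAE |
| New IOP rise after the first dose | TEAE | TEAE |
| Other AE ongoing at first dose that worsens afterwards | TEAE (worsening clause) | Not a TEAE if read literally; listings only |

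The definitions disagree in the first and last rows. The first row applies equally to any other AE found before dosing and dated to Visit 3.

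The last row cannot be the treated IOP rise. Section 6.1.3 allows randomization only once pressure is normal, and exclusion criterion 3 bars IOP of 21 mmHg or more at Visit 3. A later rise is therefore a new event, which is the third row, where the definitions agree.

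**Step 2. Size per event.** The plan states no figure on this point to reproduce. Group size (Section 8.3): 588 × 2/6 = 196. The AE denominator is the safety population, taken here as about 196.

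- One added subject: 1/196 = 0.51 points, if that subject is not already counted.
- Two added subjects: 2/196 = 1.02%. If the 1% cut is read per group, that is enough to pass it with no post-dose event.

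**Step 3. Effect on the interval.** The documents give neither a Visit 3 intervention rate nor an IOP AE rate, so the counts below are assumptions. Take 4 genuine post-dose IOP AEs on one active regimen and 2 on vehicle, and add k pre-dose events per group in different subjects.

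Formula: d ± 1.96 × √[p1(1−p1)/196 + p2(1−p2)/196], with p1 = (4+k)/196 and p2 = (2+k)/196.

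For k = 0: p1 = 2.04%, p2 = 1.02%, d = 1.02 points, half-width 2.43, interval −1.41 to 3.45.

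| k per group | Rates | d (points) | 95% CI | Half-width |
|---|---|---|---|---|
| 0 | 2.04% vs 1.02% | 1.02 | −1.41 to 3.45 | 2.43 |
| 2 | 3.06% vs 2.04% | 1.02 | −2.10 to 4.14 | 3.12 |
| 4 | 4.08% vs 3.06% | 1.02 | −2.65 to 4.69 | 3.67 |
| 10 | 7.14% vs 6.12% | 1.02 | −3.91 to 5.95 | 4.93 |
| 20 | 12.24% vs 11.22% | 1.02 | −5.35 to 7.39 | 6.37 |

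The k = 0 row is the 8.5.1.2 result; the other rows are the 7.1 result.

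**Step 4. Chance imbalance.** These events precede randomization, so their expected difference between groups is zero. The SD of the chance difference is √[2s(1−s)/196] for an assumed event rate s: 1.01 points at s = 1%, 2.20 at 5% and 3.03 at 10%. For example, 6 pre-dose events on active and 2 on vehicle turn the 1.02-point difference into 3.06 (−0.60 to 6.72). The reverse split gives −1.02 (−4.69 to 2.65).

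**The case against.** Several points on the other side have force.

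- **Section 7.1 can be read by clock time.** It sets the start date against the first dose, not expressly against the date of that dose. On a clock-time reading, an event resolved before randomization is excluded under both definitions. This reading is possible but not the natural one: the text speaks of a start date, and Section 7.3 names only dates. It also leaves the worsening gap open.
- **The site may date the onset to surgery day.** Visit 3 falls 18 to 34 hours after surgery. If sites do so, the IOP case disappears. That is why the point is conditional on the onset date.
- **The order of events may be recoverable.** Section 6.1.3 requires entries on several logs and the last pre-randomization IOP, and the eCRF, which is not supplied, may hold times. This would help in classifying the event, but it does not say which definition to apply.
- **Worsening could be logged as a new AE.** Section 7.1 allows progression of an underlying disease to be an AE, and such an entry would occur after the dose. This narrows the second gap but depends on how sites choose to record.
- **Measured IOP is analysed separately.** Section 8.5.1.2 plans IOP summaries by visit, changes of at least 5 and 10 mmHg from screening and from Visit 3, and values of 30 mmHg or more. None of these uses the TEAE definition. This stands fully.

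A reader might infer that extra pre-dose events could hide a real steroid effect on IOP. The documents do not support that. The TEAE intervals are descriptive and carry no hypothesis or decision rule, all the rates are assumed, and the measured-IOP tables would still show such an effect. A reader might also infer that a treated Visit 3 spike that worsens on drug is lost from the tables. Step 1 shows why it is not.

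**Conclusion.** The inconsistency is real and minor. The current text holds two TEAE definitions that give different counts for two kinds of event, and nothing supplied settles which one governs.

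For an IOP rise treated and resolved before randomization, the disagreement arises only if the onset is dated to Visit 3 and 7.1 is read by date. Each such subject then adds 0.51 points to that group's ocular TEAE rate and widens the interval. No bias between groups is expected, only chance imbalance. The total effect cannot be stated, because the documents do not say how many such events to expect; the intervals in the working illustrate assumed counts only.

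For other AEs still ongoing at first dose, 8.5.1.2 taken literally moves post-dose worsening to the listings, while 7.1 keeps it in the tables. Here 7.1 is the sounder rule.

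The primary efficacy analyses, the error control and the measured-IOP summaries do not depend on any of this.

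**What to change.** Use one definition in Section 7.1, Section 8.5.1.2 and the synopsis: onset after the first dose, or worsening after the first dose.

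For AEs with an onset on the date of Visit 3, add one eCRF item recording whether onset was before or after the first dose, and count unknowns as treatment-emergent.

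State in Section 6.1.3 that an IOP rise resolved before randomization is not treatment-emergent, and that any later rise in that eye is a new AE.

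The cost is one aligned sentence in three places, a clarification in 6.1.3, and one extra item for a limited set of AEs. The downside is that a wrong answer of before would remove a true on-treatment event from the tables; counting unknowns as treatment-emergent limits that risk but does not remove it.

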#### 6.1.4 Visit 4: Postoperative Day 3 ( $\pm 1$ Day)

***NOTE: Post-surgery visits should be scheduled so that IOP can be assessed within  $\pm 2$  hours of the time of IOP assessment on Visit 1.***

- Perform a clinical assessment of ocular symptoms
- Perform assessment of pin-holed Snellen VA
- Perform biomicroscopy assessment
- Perform IOP measurement
  - IOP should be assessed within  $\pm 2$  hours of the time IOP was assessed at Visit 1 (Screening). Measurement of IOP must occur after the assessment of ocular symptoms and biomicroscopy.
- Collect and record AEs and changes in concomitant medications
- Collect and review the Study Drug Administration Diary for accuracy and compliance. Dispense a new Study Drug Administration Diary. Instruct the subject to record the time of each instillation in the diary and to bring the diary and study drug (all bottles) to the next visit. Remind the subject that no other information should be recorded on the diary.
- Remind the subject to instill 1 drop of study drug into the study eye according to the instructions provided with the kit. For those subjects receiving a topical antibiotic, remind the subject that the topical antibiotic drops must be instilled a minimum of 15 minutes BEFORE study drug application.

**NOTE: Subjects will be assessed at Visits 4 through 7 (Postoperative Days 3, 8, 15, and 18) for treatment rescue. Subjects with worsening or no change in the grade of inflammation in the study eye compared with the previous visit are eligible and may be considered for rescue medication at the discretion of the Investigator. The choice of rescue medication and dosing shall be determined by the Investigator. See Section 6.2.3.1 for more details.**

6.1.5 Visit 5: Postoperative Day 8 ( $\pm$  1 Day)

**NOTE: Post-surgery visits should be scheduled so that IOP can be assessed within  $\pm$  2 hours of the time of IOP assessment on Visit 1.**

- Perform a clinical assessment of ocular symptoms
- Perform study drug sensation assessment
- Perform assessment of pin-holed Snellen VA
- Perform biomicroscopy assessment
- Perform IOP measurement
  - IOP should be assessed within  $\pm$  2 hours of the time IOP was assessed at Visit 1 (Screening). Measurement of IOP must occur after the assessment of ocular symptoms and biomicroscopy.
- Collect AEs and changes in concomitant medications
- Collect and review the Study Drug Administration Diary for accuracy and compliance. Dispense a new Study Drug Administration Diary. Instruct the subject to record the time of each instillation in the diary and to bring the diary and study drug (both bottles) to the next visit. Remind the subject that no other information should be recorded on the diary.
- Remind the subject to instill 1 drop of study drug into the study eye according to the instructions provided with the kit. For those subjects receiving a topical antibiotic, remind the subject that the topical antibiotic drops must be instilled a minimum of 15 minutes BEFORE study drug application
- Remind the subject that the last instillation of study drug will occur the evening before Visit 6. If the subject doses on the day of Visit 6 the visit should be performed as scheduled.

6.1.6 Visit 6: Postoperative Day 15 ( $\pm$  1 Day) (End of Treatment Period)

**NOTE: Post-surgery visits should be scheduled so that IOP can be assessed within  $\pm$  2 hours of the time of IOP assessment on Visit 1.**

- Perform a clinical assessment of ocular symptoms
- Perform assessment of pin-holed Snellen VA
- Perform biomicroscopy assessment

- Perform IOP measurement
  - IOP should be assessed within  $\pm 2$  hours of the time IOP was assessed at Visit 1 (Screening). Measurement of IOP must occur after the assessment of ocular symptoms and biomicroscopy.
- Perform dilated fundus examination
- Collect and record AEs and changes in concomitant medications
- Collect and review the Study Drug Administration Diary for accuracy and compliance
- Collect all used and unused study drug (all bottles) from the subject

